### 2.2.1. Clinical Experience with Sotrovimab

As of 18 August 2021, a total of 1843 participants have received sotrovimab (500 mg dose) administered IV or intramuscularly in the Vir/GSK-sponsored clinical studies. Sotrovimab has been well tolerated when administered both intravenously and intramuscularly with no serious safety concerns identified to date. A summary of serious adverse event (SAE) and other safety data are included for these studies in the sotrovimab Investigator's Brochure.

Sotrovimab received Emergency Use Authorization in the US based on the results from COMET-ICE, a seamless FIH/Phase 2/3 study assessing the safety and efficacy of a single 500 mg IV dose of sotrovimab for the early treatment of COVID-19 in non-hospitalized participants at high risk for progression and subsequent hospitalization. Based on the results from COMET-ICE, temporary Authorizations have also been granted for sotrovimab in several countries, including Canada (Interim Order), Singapore (Pandemic Special Access), United Arab Emirates, Bahrain, Kuwait, Oman, Qatar, Thailand, and Brazil; provisional/conditional marketing approval has been granted in Australia, Saudi Arabia, United Kingdom, Japan and Switzerland; and full marketing approval has been granted in the European Union.

Other ongoing Vir/GSK-sponsored studies include a Phase 2 COMET-PEAK safety, PK, and virology study in early treatment (VIR-7831-5006/GSK Study 216912; NCT04779879), a Phase 3 COMET-TAIL study of intramuscular injection for early treatment (VIR-7831-5008), a Phase 2 study COMET-PACE study in pediatric participants for early treatment (VIR-7831-5005), and a Phase 1 pharmacokinetic (PK) study with healthy Japanese participants (VIR-7831-5009/GSK Study 217653; NCT04988152). In addition, Vir/GSK supported clinical studies (ACTIV-3-TICO [VIR-7831-5004, GSK Study 215149], BLAZE-4 [VIR-7831-5007, 217079]) are evaluating sotrovimab as a single agent or in combination. A summary of SAE and other safety data are included for these studies in the sotrovimab Investigator's Brochure (IB).

Sotrovimab at 1000 mg IV is also being evaluated in the UK-based RECOVERY platform trial, where hospitalized participants with confirmed COVID-19 are randomized to receive different candidate therapies. The RECOVERY Trial Independent Data Monitoring Committee's 04 March 2022 review of safety and efficacy data, inclusive of 568 participants that received 1 g IV sotrovimab, suggested no reason to modify the protocol.

To date, partial Gen 2 IV PK is available from BLAZE-4 (NCT04634409), COMET-PEAK (NCT04779879) and the Japan PK Study (NCT04988152).

### 2.3. Benefit/Risk Assessment

## 2.3.1. Risk Assessment

Potential Risk of Clinical Significance	Summary of Data/Rationale for Risk	Mitigation Strategy
Study Intervention: Sotrovimab		
Infusion reactions including hypersensitivity reactions (HSR)	
While sotrovimab is a fully human IgG, Systemic reactions (SR), including hypersensitivity reactions, are a potential general risk associated with the mAb class of therapeutics.
 
Given the totality of pre-clinical and clinical data to date it is the Sponsor's position that a up to 3000 mg dose may be safely used in individuals with mild to moderate COVID-19.
 
There was no evidence of systemic infusion reactions in toxicology studies were conducted with sotrovimab in monkeys.
 
Available safety data from the clinical development program comes from evaluation of a 500 mg dose of sotrovimab administered by IV infusion, a 500 mg and a 250 mg dose administered by IM injection for early treatment of COVID-19, and a 1000 mg dose currently being evaluated in an ongoing clinical study in hospitalized participants with severe COVID-19. Safety data from the clinical program to date have demonstrated a low rate of adverse events at the time of Day 29 analysis, particularly SAE and Grade 3-4 AEs. The COMET-ICE (Phase 2/3) and COMET-TAIL (Phase 3) studies demonstrated infrequent Grade 3 and 4 AEs and SAEs in the treatment groups.
 
COMET-TAIL did not demonstrate a pattern of incrementing safety findings associated with increasing dose or exposure as it compared 250 mg IM to 500 mg IM and 500 mg IV dosing.
	
Participant selection: Participants will be excluded if they have a history of hypersensitivity to any of the excipients present in the investigational product.
 
Monitoring:
 
 
During the Lead-In phase, participants will be monitored regularly at 15 minutes, 30 minutes, 45 minutes, 1 hour, and 2 hours post-administration of study treatment (including vital signs, see the SoA in Section 1.3). Post-infusion monitoring time will only be reduced to 1 hour for additional participants enrolled after the lead in phase is complete.
 
A Joint Safety Review Team (JSRT) review will be conducted at regular intervals, inclusive of active monitoring of lead-in data. 
 
JSRT will review safety data before completing full cohort enrollment (after lead in phases), before any dose escalation (to review safety of the dose just prior to it) and before any decreases in infusion times (to review safety of the infusion time just prior to it)
 
 
 


VIR-7831  
Vir Biotechnology, Inc.

VIR-7831-5008 (GSK Study 217114)  
Amendment 4

Potential Risk of Clinical Significance	Summary of Data/Rationale for Risk	Mitigation Strategy
	
In the COMET-ICE study in participants with mild/moderate COVID-19 at high risk of progression, IRRs that occurred within 24 hours post infusion (pyrexia, chills, dizziness, dyspnea, pruritus, rash, and other infusion-related reaction) were reported in 6 (1%) of participants in the sotrovimab arm and 6 (1%) of participants in the placebo arm. All IRRs were nonserious, and Grade 1 or 2 severity and none led to treatment pausing or discontinuation. In the sotrovimab arm, all of the cases of IRRs were considered resolved and in the placebo arm, one participant had an event considered not resolved at the time of data cut-off. In COMET-ICE, all HSRs observed in the study were nonserious, of Grade 1 (mild) or Grade 2 (moderate) severity and reported in 2% of participants who received sotrovimab and in <1% who received placebo (9 participants treated with sotrovimab; 5 participants treated with placebo). None of the reactions in either arm led to pausing or discontinuation of the infusions. All events across both treatment groups were reported as resolved or resolving at the time of data cut-off.
 
No anaphylaxis events were reported in the COMET-ICE study in participants with mild to moderate COVID-19 not requiring hospitalization at study entry.
 
No anaphylaxis or serious hypersensitivity reactions were reported in the COMET-TAIL study in participants with mild to moderate COVID-19 not requiring hospitalization at study entry.
	
 
Investigational product will be administered in the clinic with staff trained in emergency care and resuscitation procedures with emergency care kit on hand during the study intervention administration and post-therapy observation periods.
 
Investigators will be instructed to discontinue IV infusions for participants who develop Grade 3 or higher infusion reactions.
 
If a participant experiences a Grade 2 IRR, investigators will be instructed to pause the infusion. The infusion may subsequently resume at a slower pace, at the investigator's discretion, and/or after symptomatic treatment (eg, antihistamines, IV fluids).
 
Infusion-related reactions including HSRs will be categorized as AESIs (as has been done in the past for other studies).
 

VIR-7831  
Vir Biotechnology, Inc.

VIR-7831-5008 (GSK Study 217114)  
Amendment 4

Potential Risk of Clinical Significance	Summary of Data/Rationale for Risk	Mitigation Strategy
	
A potentially life-threatening allergic reaction (anaphylaxis) was observed in 1 adult participant who received sotrovimab in the study of individuals hospitalized with COVID-19 (the ACTIV-3-TICO study). The anaphylaxis was considered by the investigator to be related to study intervention. The participant was treated for the allergic reaction and recovered.
 
Additional cases of anaphylaxis after dosing have been reported from post-marketing pharmacovigilance.
 
The RECOVERY trial is a pragmatic platform clinical trial evaluating different treatments in hospitalized participants with serious COVID-19 and is currently ongoing in the UK. Given the pragmatic nature of the trial, limited safety data are collected during the course of the study with the focus being on SAEs that are believed to be related (with reasonable possibility) to the study treatment. RECOVERY is not a GSK/Vir sponsored trial, and therefore Vir does not currently have direct access to the blinded safety data from this study. However, a trial DMC letter dated 11 May 2022 noted that recruitment is ongoing and as of 2 May 2022, 996 participants had been randomized 1:1 (sotrovimab: standard of care). This trial DMC letter (dated 11 May 2022) also confirmed that review of safety data on 996 patients (1:1 sotrovimab: standard of care) was completed and that the trial may continue with no changes in conduct [DMC Report 2022]. The RECOVERY team has confirmed that up to the 21 March 2022 there has been only 1 related SAE reported. This was a case of suspected allergic reaction treated with adrenaline. The participant apparently improved within 2 hours without further complication and was discharged 5 days later.
	

VIR-7831  
Vir Biotechnology, Inc.

VIR-7831-5008 (GSK Study 217114)  
Amendment 4

Potential Risk of Clinical Significance	Summary of Data/Rationale for Risk	Mitigation Strategy
Enhanced risk of systemic reactions including hypersensitivity reactions (SR/HSR) due to higher dose levels	
See "Infusion reactions including hypersensitivity reactions (HSR)"
 
It is possible that the risk of infusion reactions may be enhanced due to increase doses used, however as noted in the dose justification: the no-observed-adverse-effect-level for VIR-7831 was established when VIR-7831 was administered via IV infusion at 500 mg/kg (the highest dose tested) once a week for 2 weeks in cynomolgus monkeys (TX-7831-0102). Based on a preliminary population PK model for sotrovimab, the predicted <math>AUC_{inf}</math> following a 2000 mg IV dose is 21,400 <math>\mu\text{g}^*\text{day}/\text{mL}</math> and predicted <math>C_{max}</math> is 636 <math>\mu\text{g}/\text{mL}</math>. Based on the proposed 2000 mg IV dose, the margins based on nonclinical <math>C_{max}</math> and <math>AUC</math> margins of 21- and 10x, respectively, support the proposed clinical dose of 2 g IV. The <math>AUC_{inf}</math> following a 3 g IV dose is 32,100 <math>\mu\text{g}^*\text{day}/\text{mL}</math> and predicted <math>C_{max}</math> is 954 <math>\mu\text{g}/\text{mL}</math>. Based on the proposed 3000 mg IV dose, the margins based on nonclinical <math>C_{max}</math> and <math>AUC</math> margins of 14- and 7x, supporting the proposed doses up to 3000 mg.
	See Mitigation Strategy for "Infusion reactions including hypersensitivity reactions (HSR)"
Enhanced risk of systemic reactions including hypersensitivity reactions (SR/HSR) due to decreased infusion times	
See "Infusion reactions including hypersensitivity reactions (HSR)"
 
It is possible that decreased infusion times in Cohort B1 (30-minute infusion time of 2000 mg) and B2 (15-minute infusion time of 2000 mg) may enhance the possibility of a systemic reaction including hypersensitivity reactions (SR/HSR)
	See Mitigation Strategy for "Infusion reactions including hypersensitivity reactions (HSR)"

VIR-7831  
Vir Biotechnology, Inc.

VIR-7831-5008 (GSK Study 217114)  
Amendment 4

Potential Risk of Clinical Significance	Summary of Data/Rationale for Risk	Mitigation Strategy
Immunogenicity	
While sotrovimab is a fully human IgG, the development of anti-drug antibodies (ADA) that have the potential to impact safety and/or efficacy are a potential general risk associated with the mAb class of therapeutics.
	
Monitoring: This study will include participant follow-up for a period of 36 weeks to assess for the potential of immunogenicity (measurement of ADA) as well as if ADA is potentially causally associated with specific safety concerns and/or impact efficacy.

Antibody Dependent Enhancement (ADE) due to sub-neutralizing levels of sotrovimab enhancing fusion or leading to Fc $\gamma$ R mediated increased viral uptake and replication with virus production	
This is a concern related to the potential for participants with sub-neutralizing mAb levels to experience a higher incidence of infection and/or more severe disease compared to participants with no circulating mAb and/or established protective immunity to SARS-CoV-2.
 
ADE associated with Dengue virus 1-4 serotype infections is one of the most widely cited examples in which reinfection with a different serotype can, in a minority of participants, run a more severe course in the setting of limited antibodies generated by prior infection.
 
The potential for enhanced disease in this setting is due to increased uptake of virus by FcR-expressing cells, such as macrophages, and increased viral replication in these cells. Recent data shows that SARS-CoV-2 does not replicate efficiently in macrophages [Hui 2020], suggesting minimal to no risk of ADE via this mechanism.
 
As of 10 March 2021, the COMET ICE study enrollment has been stopped based profound efficacy on the recommendation of IDMC. The total of 1057 participants have been randomized to either the IV infusion of sotrovimab Gen1 (500 mg dose) or placebo. Based on the Joint SRT review of blinded data, there has been no confirmed events of ADE.
	
Monitoring: There is a safety lead in of 30 subjects for the initial 2000 mg and 3000 mg cohorts (Cohorts A and C) to aid in early detection of ADE.
 
We recognize that ADE may not present until later time points, thus this study will include participant follow up for a period of 36 Weeks to assess for the potential of enhanced disease in the context of waning sotrovimab levels.
 
Assessments for unusually severe disease in mAb-treated participants will be performed by the JSRT to assess for unusually severe disease in mAb-treated participants. Re-infection will be assessed as new SAEs related to COVID-19 infection during follow up period.

VIR-7831  
Vir Biotechnology, Inc.

VIR-7831-5008 (GSK Study 217114)  
Amendment 4

Potential Risk of Clinical Significance	Summary of Data/Rationale for Risk	Mitigation Strategy

ADE due to enhanced disease pathology from viral antigen-antibody related immune complex deposition or complement activation and immune cell recruitment in target organs
	
There is the possibility that a large amount of antibody that binds, but does not neutralize, virus in the presence of a high viral load could result in immune complex deposition and complement activation in tissue sites of high viral replication, such as the lungs, vascular endothelia, renal or cardiovascular tissue [Hamming 2004], leading to tissue damage/immune complex disease
 
This is hypothesized to have contributed to inflammation and airway obstruction observed in the small airways of infants who received a formalin-inactivated (FI) respiratory syncytial virus (RSV) vaccine [Polack 2002] and in a few cases of fatal H1N1 influenza infection [Wu 2010]
 
The potential for enhanced disease in this setting may be due to low affinity or cross-reactive antibodies with poor or no neutralizing activity.
 
Triggering of cytokine release by antibody-virus-FcYR interactions although usually highly beneficial due to their direct antiviral effects and immune cell recruitment to control viral spread in tissues, also has the potential to enhance pathologic changes initiated by the viral infection.
 
Observational data from 20,000 COVID-19 participants treated with convalescent plasma, although not placebo controlled, is suggestive that even polyclonal mixtures of neutralizing and non-neutralizing antibodies can be safely administered [Joyner 2020]
 
Sotrovimab shows potent binding in vitro as well as neutralization of pseudovirus and live virus thus this risk is deemed to be low.
 
In clinical studies to as of May 2022 there has been no evidence of ADE associated with sotrovimab.
	
Monitoring:
 
This study will include participant follow-up for a period of 36 weeks to assess for the potential of enhanced disease in the context of waning sotrovimab levels.
 
Periodic review of clinical signs and symptoms of COVID-19, clinical chemistry, AEs, end-organ disease and histopathological diagnoses will be performed by the JSRT to identify potential cases of immune complex disease.
 
Assessments for unusually severe disease in mAb-treated participants will be performed by the JSRT. Re-infection will be assessed as new SAEs related to COVID-19 infection during follow-up period.

VIR-7831  
Vir Biotechnology, Inc.

VIR-7831-5008 (GSK Study 217114)  
Amendment 4

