## 8.4. Adverse Events (AEs), Serious Adverse Events (SAEs) and Other Safety Reporting

The definitions of adverse events (AE) or serious adverse events (SAEs) can be found in [Section 10.3](#).

The definitions of unsolicited and solicited adverse events can be found in [Section 10.3](#).

AEs will be reported by the participant (or, when appropriate, by a caregiver, surrogate, or the participant's legally authorized representative).

Hospitalization or death are typically considered SAEs and they are included in the primary endpoint. However, if a hospitalization or adverse event is related to expected progression, signs, or symptoms of COVID-19 (as detailed in [Section 8.4.8](#)) or if hospitalization is due to elective treatment of a pre-existing condition that did not worsen from baseline as noted in [Section 10.3](#) it will not be considered as an SAE. These events will be collected and reported as SAEs only if the event is more severe than expected for the participant's current clinical status and medical history or if the investigator feels that it is related to study drug. These will be collected and reported as SAEs as delineated in [Section 8.4.1](#) below. Since it will not be possible to delineate in a single participant whether the hospitalization is directly related to COVID-19 complications or could be related to sotrovimab causing more severe disease due to ADE, all hospitalizations for management of acute illness, regardless of cause, will be included in the primary endpoint.

The investigator and any qualified designees are responsible for detecting, documenting, and reporting events that meet the definition of an AE or SAE and remain responsible for following up AEs that are serious, considered related to the study intervention or the study, or that caused the participant to discontinue the study (see [Section 7](#)). As noted in [Section 8.2.1](#) data on hospitalization or death should additionally be recorded in the eCRF for all relevant sections.

The method of recording, evaluating, and assessing causality of AEs and SAEs and the procedures for completing and transmitting SAE reports are provided in [Section 10.3](#).

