#### **8.4.8. Disease-Related Events and/or Disease-Related Outcomes Not Qualifying as AEs or SAEs**

Adverse events related to expected progression, signs, or symptoms of COVID-19, unless more severe than expected for the participant's current clinical status and medical history, or resulting in hospitalization as noted in Section 8.4, should not be reported as an AE or SAE.

However, if the underlying disease (i.e., progression) is greater than that which would normally be expected for the clinical course of the disease and/or the patient's clinical status, or if the investigator considers that there was a causal relationship between treatment with study treatment(s) or protocol design/procedures and the disease progression, then this must be reported as an AE or SAE.

For example, the following constitute events NOT meeting the AE definition and that should be considered as expected progression, signs, or symptoms of COVID-19:

- hypoxemia due to COVID-19 requiring supplemental oxygen
- hypoxemia due to COVID-19 requiring non-invasive ventilation or high flow oxygen devices
- respiratory failure due to COVID-19 requiring invasive mechanical ventilation or extracorporeal membrane oxygenation (ECMO)

**NOTE:** If either of the following conditions apply, then the event must be recorded and reported as an AE or SAE (instead of a disease-related event):

- The event is, in the investigator's opinion, of greater intensity, frequency, or duration than expected for the natural history of the disease, or
- The investigator considers that there is a reasonable possibility that the event was related to treatment with study treatment(s).

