#### 8.4.9.3. Antibody Dependent Enhancement

Antibody-dependent enhancement (ADE) of disease theoretically can occur via one of three previously described mechanisms:

1. By facilitating viral entry into host cells and enhancing viral replication in these cells
2. By increasing viral fusion with target host cells, enhancing viral replication in these cells
3. By enhancing disease pathology from viral antigen-antibody related immune complex deposition or complement activation and immune cell recruitment in target organs

The first two mechanisms are hypothesized to occur at sub-neutralizing antibody concentrations (Arvin 2020). This study will include participant follow-up for a period of 5 half-lives to assess for the potential of enhanced disease in the context of waning sotrovimab levels, which may manifest as an increased incidence of re-infection or increased severity of re-infections after recovery from initial illness. The third mechanism is hypothesized to occur at high levels of antigen (i.e., viral load) and antibody potentially leading to immune complex deposition and complement activation in tissue sites of high viral replication. This may manifest as acute deterioration temporally associated with sotrovimab dosing or as increased severity or duration of illness in sotrovimab-treated participants vs. placebo-treated participants.

As of 10 March 2021, enrollment into the COMET ICE study, evaluating sotrovimab for the treatment of non-hospitalized individuals with mild to moderate COVID-19, has been stopped based on the recommendation of IDMC. The total of 1057 participants have been randomized to either the IV infusion of sotrovimab Gen1 (500 mg dose) or placebo. Based on the Joint SRT review of blinded data, there has been no confirmed events of ADE. The ACTIV-3 TICO study of sotrovimab treatment in hospitalized participants with COVID-19 symptoms, which was terminated due to futility, did not reveal any safety concerns overall and no ADE. The COMET TAIL study did not reveal any safety concerns overall and no ADE.

As described in [Section 2.3.1](#), AEs potentially related to ADE of the disease will be reviewed by the JSRT to see if there are unusually severe manifestations of COVID-19 in treated individuals.

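### The protocol relies on SAE reports to find COVID-19 re-infection, but its exclusion of expected COVID-19 events from SAE reporting is not limited to the index illness, so later re-infection admissions can be classified inconsistently

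*Protocol*

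**What the plan says.** The risk table in Protocol Section 2.3.1 treats ADE under waning antibody as a late risk and extends follow-up to 36 weeks for that reason. The row on sub-neutralizing levels states: "Re-infection will be assessed as new SAEs related to COVID-19 infection during follow up period". The row on immune-complex disease says the same: "Re-infection will be assessed as new SAEs related to COVID-19 infection during follow-up period".

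The reporting rules read differently. Section 8.4 provides that "if a hospitalization or adverse event is related to expected progression, signs, or symptoms of COVID-19" then "it will not be considered as an SAE". The way back is narrow: "These events will be collected and reported as SAEs only if the event is more severe than expected" for the participant, or if the investigator attributes the event to study drug. Section 8.4.8 covers "Adverse events related to expected progression, signs, or symptoms of COVID-19, unless more severe than expected" and says such events are not to be reported as AEs or SAEs. Its examples start with "hypoxemia due to COVID-19 requiring supplemental oxygen" and extend to invasive ventilation and ECMO. Appendix 3 (Section 10.3.1) repeats the exclusion for the disease under study.

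Section 8.4.9.3 explains why re-infection matters. ADE at low antibody levels "may manifest as an increased incidence of re-infection or increased severity of re-infections after recovery from initial illness".

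**The concern.** The risk table assumes that a COVID-19 re-infection serious enough to count will arrive as an SAE. The reporting rules remove COVID-19 events of expected course from SAE reporting, and they give no end date, no recovery criterion and no reference to the first episode. Excluding the expected course of the disease being treated is sensible. That reason does not carry over to a new infection months after recovery.

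What is at stake is the count of re-infection admissions of ordinary severity. Section 8.4.9.3 names incidence of re-infection, as well as severity, as a possible ADE sign. An incidence signal consists largely of unremarkable cases, and those are the ones the exclusion can remove. The substudy has no placebo arm, so any comparison would be across cohorts or with outside data. Either comparison needs all sites to count in the same way.

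**Working it through.** The plan states no figure to reproduce. The check sets the passages side by side and compares the collection windows.

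**Test case.** A participant recovers, is re-infected at Week 20 and is admitted with ordinary COVID-19 hypoxemia that the investigator considers expected and unrelated to sotrovimab.

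| Protocol section | Classification of this admission |
|---|---|
| 2.3.1 (two rows) | New COVID-19 SAE |
| 8.4 | Not an SAE: hospitalization related to expected COVID-19, no override met |
| 8.4.8 | Unclear: hypoxemia needing oxygen is a listed non-AE, but the sentence also mentions events leading to admission and points back to 8.4 |
| 8.2.1 | An SAE form is listed among the data to capture for a hospitalization |
| 10.3.1 (Appendix 3) | Not an AE if read as the disease under study; an AE if read as a new condition diagnosed after dosing |

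The admissions clause in 8.4.8 has two readings. It can exempt hospitalized events from the exclusion, or it can bring them into it by reference to 8.4, which excludes them. The text does not settle which.

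**Windows** (Sections 3 and 8.4.1).
- AE collection, and the AE, AESI and DRE endpoints: to Week 12.
- SAE endpoint: to Week 36.
- All-cause hospitalization-or-death composite (exploratory): to Day 29.
- Period in which SAEs are the only safety endpoint: 36 − 12 = 24 weeks, and 24/36 = two thirds of follow-up.

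In those 24 weeks the test-case admission is outside the AE window, the DRE endpoint and the efficacy composite. Under 8.4 it is also outside the SAE definition.

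**Section 8.4's own safeguard.** That section accepts that COVID-19 complications and ADE cannot be told apart in a single participant, and answers by counting all acute-illness hospitalizations in the primary endpoint. In this substudy the primary endpoint is AEs, SAEs, AESIs and DREs through Day 8 (Section 3), so the safeguard does not reach a later re-infection.

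**Illustration.** The re-infection and admission rates are assumptions; the documents give none. Admissions after Day 29 = N × re-infected × admitted.
- N = 500: 500 × 10% × 4% = 2; 500 × 20% × 5% = 5.
- N = 200 (Cohort A only): 200 × 10% × 4% = 0.8; 200 × 20% × 5% = 2.

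The 2.3.1 rule counts all of these as SAEs. The 8.4 rule counts none if every one is judged expected and unrelated, which is the extreme case. Any that fall before Week 12 could still appear as DREs.

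**The case against.** The strongest reply is that the exclusion was meant for the index illness and can be read that way. Section 8.4.8 refers to the underlying disease and its clinical course. Section 10.3.1 makes newly diagnosed conditions after dosing AEs. Section 8.4.9.3 separates re-infection from the initial illness. On that reading a Week 20 re-infection is a new condition and 2.3.1 is correct. The intent is plausible, but no section states it, and the wording about signs or symptoms of COVID-19 covers a second episode as readily as the first.

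The second reply is that re-infections are recorded whatever their SAE status, and this stands. Section 8.2.2 has calls at Weeks 8, 16, 28, 32 and 36 that ask about a new diagnosis, healthcare encounters and medications. The Schedule of Activities adds clinic visits for the same purpose. Section 8.2.1 captures admission and ICU dates and respiratory support, and Section 8.4.7 requires death forms regardless of SAE status. A reader might infer that re-infection admissions are lost to the study; they are not. The gap is in classification and counting. Subsequent COVID-19 illness is not an endpoint in Section 3. The supplied SAP, based on Amendment 3, specifies no summary of it, although the substudy's own analysis plan was still to be finalized.

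The third reply is that severe cases are protected. This also stands: re-infections judged more severe than expected or drug-related remain SAEs, so the severity signal is largely kept. The incidence signal is not.

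**Conclusion.** The inconsistency is real and needs no assumed rate. Section 2.3.1 and Section 8.4 give opposite classifications for a re-infection admission of expected severity, and Sections 8.2.1, 8.4.8 and 10.3.1 leave sites room to go either way. Between Weeks 12 and 36 such an admission can be missing from the only safety endpoint still open.

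Two stronger readings go too far. One is that sites are bound to apply Section 8.4.8. The documents set no such order of precedence, 8.4.8 is itself ambiguous on admissions, and the clear exclusion of hospitalizations comes from 8.4. The other is that the SAE endpoint would show no re-infections whatever the true number. That would require every admission to be judged both expected and unrelated, at sites that all follow 8.4.

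The size is small in absolute terms: 2 to 5 admissions at N = 500, or about 1 to 2 at N = 200, as worst cases on assumed rates. N = 500 also requires every optional cohort to open. The point is worth correcting because at counts this low a site-dependent rule can determine whether an incidence signal is seen.

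**What to change.** Reconcile Sections 2.3.1, 8.2.1, 8.4, 8.4.8 and 10.3.1 with one rule:

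- The disease-related-event exception applies only to the index COVID-19 episode, with the end of that episode (recovery) defined in advance.
- A new COVID-19 episode after recovery that meets a seriousness criterion is reported as an SAE through Week 36, whether or not its course is expected.
- A non-serious new episode is an AE only within the Week 12 AE window. After that it is recorded through the Section 8.2.2 calls and the matching clinic visits.
- The hospitalization clause in 8.4.8 is reworded to have one meaning, and the SAE form entry in 8.2.1 is aligned with it.

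Section 2.3.1 would then be accurate for serious re-infections. The summary of COVID-19-related SAEs beyond Day 8, already planned in Section 9.4.4, could carry the count without a new analysis. The cost is a wording change in several sections, an instruction to sites and a few more SAE reports.
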